**Revision History**

	[REDACTED]		[REDACTED]	[REDACTED]		[REDACTED]	[REDACTED]
	[REDACTED]		[REDACTED]	[REDACTED]		[REDACTED]	[REDACTED]
	[REDACTED]		[REDACTED]	[REDACTED]		[REDACTED]	[REDACTED]

**PROTOCOL SUMMARY OF CHANGES**

Revision	Section	Description and Rationale for Change	Location of Change
A	N/A	Original	N/A
B	N/A	The protocol was revised to include a second cohort of subjects who did not receive hypotensive medication washout prior to treatment	Throughout the Protocol
	Synopsis & Section 2	Study Objective : Revised this section to specify the subjects who will be enrolled and observed in the study	Pages 6 and 10
	Synopsis & Section 6.2	Effectiveness Endpoints: Revised the effectiveness endpoints to reflect how study endpoints will be reviewed for the second cohort	Pages 7 and 14
	Synopsis & Section 7.1	Inclusion Criteria: Elaborated on inclusion criterion # 1 to reflect the second cohort	Pages 8 and 14
	Synopsis & Section 7.2	Removed exclusion criterion # 4	Pages 9 and 15
	5	The Study Design section was revised to clarify that only subjects who underwent hypotensive medication washout prior to OMNI surgery will receive a washout of hypotensive medications at the 24- and 36-month visits, if using hypotensive medication(s) at those visits.	Page 13
	8	Revised this section to show 2 study visit schedule : One for each cohort. Table 1 to reflect a Washout visit, and Table 2 without a washout visit.	Page 16
	8.3	Revised this section to clarify the number of subjects to be enrolled in each cohort, and which subjects will receive a hypotensive medication washout	Page 18
	8.7.1	Revised this section to specify which subjects will receive a hypotensive medication washout	Page 19
	17	Revised Appendix A, to specify what procedures should be completed for each cohort: Washout of hypotensive medications, BCVA, Visual field and IOP	Pages 38-46
	N/A	Insignificant editorial changes were made to provide further clarity as needed	Throughout the Protocol

---

## 1 PROTOCOL SYNOPSIS

Protocol Title	An observational multicenter clinical study to assess the long-term safety and effectiveness of the OMNI® Surgical System in combination with cataract surgery in eyes with open angle glaucoma (Gemini 2.0)
Protocol ID Number	[REDACTED]
Study Device	OMNI® Surgical System
Study Objective	The purpose of this study is to evaluate the long-term safety and effectiveness of the OMNI® Surgical System in subjects who were treated with the OMNI Surgical System following Cataract Extraction, at least 700 days prior to enrollment.
Study Design	This is a multicenter, observational study with no planned surgical interventions. Both prospective and retrospective data on participating subjects will be collected in the study.
Primary Safety Endpoint	
 
Rate of occurrence of sight-threatening adverse events (AEs)
 

Secondary Safety Endpoints	
 
Rates of ocular AEs
 
Reduction in best corrected distance visual acuity (BCVA) from baseline
 
Secondary Ocular Surgical Interventions, including laser, for intraocular pressure (IOP) control
 

Effectiveness Endpoints	
For eyes that underwent washout prior to OMNI surgery:
 
 
• Reduction in mean unmedicated diurnal IOP (DIOP) from the preoperative unmedicated DIOP
 
• Reduction in mean number of IOP-lowering medications from screening
 
• Percent of eyes with a <math>\geq 20\%</math> reduction in unmedicated diurnal IOP from the preoperative unmedicated DIOP
 
• Percent of eyes with unmedicated diurnal IOP between 6 and 18 mmHg inclusive
 
 
For eyes that did not undergo washout prior to OMNI surgery:
 
 
• Reduction in mean medicated IOP from pre-operative medicated IOP
 
• Reduction in mean number of IOP-lowering medications from screening
 
• Percent of eyes with a <math>\geq 20\%</math> reduction in mean medicated IOP from pre-operative medicated IOP
 
• Percent of eyes with medicated IOP between 6 and 18 mmHg inclusive
 

--------------------------------	---

Inclusion Criteria	Inclusion Criteria
	
To be included in the study, individuals must meet each eligibility criterion presented as follows:
 
 
1. Treated with the OMNI Surgical System in combination with cataract extraction [REDACTED] [REDACTED]. Two cohorts will be enrolled:             
 
a. Subjects who underwent a pre-operative washout of ocular hypotensive medications with post-washout DIOP of [REDACTED] OR
 
b. Subjects without a preoperative washout of ocular hypotensive medications with pre-operative medicated IOP [REDACTED] mmHg and on [REDACTED] hypotensive medications
 
 
 
 
Note: Mild to moderate open angle glaucoma as documented in subjects' medical record substantiated using funduscopic exam or OCT and at least one visual field test.
 
The visual field test may be historical (within 6 months prior to OMNI surgery).
 
 
2. Is able to understand study requirements and willing to follow study instructions
 
3. Is willing to return for required study follow-up visits
 

Exclusion Criteria	
The presence of any of the following characteristics will exclude individuals from study participation:
 
 
• Systemic disease that, in the opinion of the Investigator, would put the subject's health at risk and/or prevent completion of required study visits
 
• Ocular pathology which, in the Investigator's judgment, would either place the subject at increased risk of complications, contraindicate washout, place the subject at risk of significant vision loss during the study period (e.g., wet age macular degeneration (AMD), corneal edema, Fuch's dystrophy, active intraocular infection or inflammation within 30 days prior to Screening Visit, etc.), or interfere with compliance to elements of the study protocol (e.g., returning to Investigator's office for follow-up visits)
 
• Women of childbearing potential if they are currently pregnant or intend to become pregnant during the study period; are breast-feeding; or are not in agreement to use adequate birth control methods to prevent pregnancy throughout the study
 

Number of Subjects Enrolled and Treated	Up to 130 subjects will be enrolled
Number of Sites	Up to 15 study sites in US
Schedule of Visits	24 Month, 36 Month

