## 5 STUDY DESIGN

This is a multicenter, observational research study with no planned surgical interventions. Both prospective and retrospective data on participating subjects will be collected in the study. Up to 130 subjects will be enrolled. Subjects will be followed from 24-months (700 – 1040 days) through 36-months (1,050 – 1,110 days) post-surgery. Pre-operative and surgery data will be collected retrospectively.

Prospective data will be collected for all study specific post-operative visits following enrollment into the study.

The study will employ a medication washout at the 24-, and 36-month endpoints for the subjects who received medication washout prior to the OMNI procedure and are using hypotensive medications at those visits.

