### **8.3 NUMBER OF SUBJECTS, DURATION OF FOLLOW-UP AND STUDY DURATION**

Up to 130 subjects will be enrolled. Eligible subjects will be enrolled at the 24-month follow up timepoint as shown by Table 1 or 2 as applicable. At least 50 subjects will be enrolled in each cohort. For subjects in cohort A, diurnal IOP measurements will be measured at both visits for those subjects who underwent medication washout and where DIOP was measured pre-operatively (Cohort A). Cohort A subjects using ocular hypotensive medication(s) at 24 and 36 months will undergo a medication washout (Table 3) and return for diurnal IOP measurements at a second visit within the same window, as shown in Table 1. There will be no diurnal IOP measurements for subjects in cohort B. IOP measurements will be measured as shown in Table 2.

It is anticipated that site initiation, recruitment and follow-up of subjects, data collection and site close-out will require approximately 60 months.

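### The exclusion for pathology that contraindicates washout also applies to Cohort B, which is never washed out on study, so Cohort B eyes can be turned away two years after surgery because of a procedure they would not undergo

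*Combined protocol and SAP*

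**What the plan says.** The exclusion list in the synopsis (Section 1) opens with "The presence of any of the following characteristics will exclude individuals from study participation". Nothing there limits a criterion to one cohort. The second bullet concerns "Ocular pathology which, in the Investigator's judgment", and the grounds that follow begin "would either place the subject at increased risk of complications, contraindicate washout, place the subject at risk of significant vision loss during the study period"; interference with compliance comes later in the same bullet.

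Eligibility is judged late. Section 8.3 states: "Eligible subjects will be enrolled at the 24-month follow up timepoint as shown by Table 1 or 2 as applicable". Section 5 and both visit schedules put that visit at Day 700 to 1,040 after surgery.

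Study washout is confined to Cohort A. Section 5 provides it "for the subjects who received medication washout prior to the OMNI procedure and are using hypotensive medications at those visits", and Section 8.7.1 repeats the restriction. For Cohort B, Section 8.3 says "There will be no diurnal IOP measurements for subjects in cohort B", Table 2 has no washout visit, and the pressure endpoints in Section 6.2 are based on medicated IOP.

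**The concern.** In Cohort A the washout ground has an obvious purpose: eyes on drops at 24 or 36 months are to be taken off them and measured. In Cohort B it has no stated purpose. A site that follows the text must reject a Cohort B eye in which stopping drops would be unsafe. A site that reads for intent may enrol the same eye. The two sites would then recruit different populations under one protocol.

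The timing adds to this. The operation took place about two years earlier, so the criterion acts on a state that the treatment and the later course of the disease may have influenced. The study's purpose is long-term safety and effectiveness in treated eyes. If the eyes removed did worse on average, the enrolled group looks better than the treated group.

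Nothing later brings these eyes back. The ITT population (Section 10.2) contains enrolled and treated subjects, the treatment-failure rule in Section 8.9.2 applies to study subjects, and subject accountability (Section 12.3) covers those enrolled. The visible text asks for no count of eyes screened and rejected.

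**Working it through.** No figure in the plan bears on this point, so there is none to reproduce. The check is a comparison of sections, followed by an illustration of size.

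**Comparison**

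| | Cohort A | Cohort B |
|---|---|---|
| Washout before surgery | Yes (inclusion 1a) | No (inclusion 1b) |
| Washout on study | Yes, if on drops (5, 8.3, 8.7.1) | None (5, 8.3, Table 2) |
| Pressure endpoints (6.2) | Unmedicated diurnal IOP | Medicated IOP |
| Medication count endpoint (6.2) | Yes | Yes |
| Washout exclusion applies (synopsis) | Yes | Yes |
| Clause serves a study procedure | Yes | No |

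The last two rows disagree for Cohort B only. The cohorts are analysed separately (Section 10.4), so the mismatch bears on Cohort B's own results.

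**Illustration of size**

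Let f be the share of otherwise eligible eyes removed by the clause, p_in the responder rate in enrolled eyes and p_out the rate the removed eyes would have had. The rate in all eligible eyes is

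p_all = (1 − f) × p_in + f × p_out,

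so the overstatement is p_in − p_all = f × (p_in − p_out).

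The documents give neither f nor the gap. Both are assumed here. Overstatement in percentage points:

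| f | Gap 20 points | Gap 40 points | Gap 60 points |
|---|---|---|---|
| 0% | 0 | 0 | 0 |
| 2% | 0.4 | 0.8 | 1.2 |
| 5% | 1.0 | 2.0 | 3.0 |
| 10% | 2.0 | 4.0 | 6.0 |
| 20% | 4.0 | 8.0 | 12.0 |

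The same formula applies to a mean. If the IOP reduction is 2 to 6 mmHg smaller in excluded eyes, the overstatement runs from 0.02 × 2 = 0.04 mmHg to 0.20 × 6 = 1.2 mmHg.

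As an outer bound, suppose no excluded eye would respond and the observed rate is 70% (assumed). The rate in all eligible eyes is then 0.70 × (1 − f): 66.5%, 63.0% and 59.5% for f of 5%, 10% and 15%.

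For scale, 35 responders among the minimum 50 eyes in a cohort (70%) have an exact 95% interval of 55.4% to 82.1%. Most of the table lies well inside that width. Selection bias, however, does not shrink as more eyes are enrolled, and the interval does not reflect it.

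**Direction**

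The sign of the gap depends on the endpoint. An eye that cannot safely stop drops is probably still using them, so its removal plausibly flatters the medication count. In Cohort A, poor unmedicated pressure is likewise a plausible companion of such a contraindication. In Cohort B the responder endpoints use medicated IOP. An eye kept on drops can reach 6 to 18 mmHg or a 20% reduction and count as a success, so there the gap may be small, zero or reversed.

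**The case against.** A reader might infer that eyes still dependent on drops fall out of the effectiveness results. The documents do not support that. The trigger is pathology in the investigator's judgment, and the bullet's examples (wet AMD, corneal edema, Fuchs' dystrophy, active infection or inflammation) are not failures of pressure control. Cohort A eyes on drops are enrolled, washed out and measured. Cohort B is analysed on medicated pressure, and medication count is an endpoint in both. The per-protocol definition in Section 10.2 even allows for 36-month medications that cannot be washed out.

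A reader might also infer that Cohort A contraindications at Day 700 mostly reflect progression since surgery, because each such eye completed a washout before it. That is possible, but no source in the documents supports it, and new pathology may have nothing to do with glaucoma control.

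Three further objections carry weight. First, the bullet's other grounds, such as risk of complications or of vision loss, may exclude many of the same eyes, so the wording change may alter few decisions. Second, recruitment is from investigators' records (Section 8.5) with no consecutive enrolment stated. Adding excluded eyes back as non-responders therefore does not give a rate in a defined population. Third, the body of Section 7.2 is missing from the text reviewed and Section 7.1 is redacted, so the scope of the clause rests on the synopsis alone.

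These objections limit the size of the point. None of them gives the washout ground a function in Cohort B.

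**Conclusion.** The mismatch holds for Cohort B: as the synopsis stands, an eye can be refused because of a procedure that cohort does not undergo, on its state two years after treatment. That alone justifies a change of wording. In Cohort A the clause serves the planned washout, and what remains is a limit on which eyes the results describe.

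The effect on results is unknown and may be nil. With a 40-point gap it is 0.8 to 8.0 points for 2% to 20% excluded, and both inputs are assumptions. A general claim that the clause raises reported effectiveness in both cohorts goes too far, because the direction is uncertain for Cohort B responder rates. The 59.5% to 66.5% range is a bound and should not be read as an estimate. The study is descriptive (Section 10.1), so no hypothesis test is at risk; what is affected is the population that the summaries describe.

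**What to change.** Reconcile the exclusion with the no-washout cohort by limiting the words on contraindicated washout to Cohort A, in the synopsis and in Section 7.2 if it reads the same. Leave the bullet's other grounds in force for both cohorts. Nobody would be washed out who is not washed out under the current text.

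Record, by cohort, the number of otherwise eligible eyes excluded under this clause, with reasons, and report it. Without that count the final report cannot show whether the selection was nil or material.

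For Cohort A, state in the report that eyes judged unfit for washout at 24 months are not represented. A table counting them as non-responders on the two percent-of-eyes endpoints is optional; if produced, label it a worst-case bound.

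The cost is one clause, one count per site and a sentence on limits. The downside is a slightly broader Cohort B whose medication results may look less favourable.

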## 2 STUDY OBJECTIVE

The purpose of this study is to evaluate the long-term safety and effectiveness of the OMNI® Surgical System in subjects who were treated with the OMNI Surgical System in combination with Cataract Extraction, at least 700 days prior to enrollment.

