## 6 STUDY ENDPOINTS

### 6.1 PRIMARY SAFETY ENDPOINT

Rate of occurrence of sight-threatening adverse events (AEs)

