### 6.2 EFFECTIVENESS ENDPOINTS

For eyes that underwent washout prior to OMNI surgery:

- Reduction in mean unmedicated diurnal IOP (DIOP) from the preoperative unmedicated DIOP
- Reduction in mean number of IOP-lowering medications from screening
- Percent of eyes with a  $\geq 20\%$  reduction in unmedicated diurnal IOP from the preoperative unmedicated DIOP
- Percent of eyes with unmedicated diurnal IOP between 6 and 18 mmHg inclusive

[figure not shown]
For eyes that did not undergo washout prior to OMNI surgery:

- Reduction in mean medicated IOP from pre-operative medicated IOP
- Reduction in mean number of IOP-lowering medications from screening
- Percent of eyes with a  $\geq 20\%$  reduction in mean medicated IOP from pre-operative medicated IOP
- Percent of eyes with medicated IOP between 6 and 18 mmHg inclusive

[figure not shown]
[figure not shown]
[figure not shown]
[figure not shown]
7 [REDACTED]

7.1 [REDACTED]

b.

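### Section 9 dates pre-existing conditions from enrolment, at least 700 days after surgery, so a persisting post-operative complication can drop out of the primary safety rate

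*Combined protocol and SAP*

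**What the plan says.** **When subjects enter.** Section 2 describes subjects operated on "at least 700 days prior to enrollment". Section 8.3 adds: "Eligible subjects will be enrolled at the 24-month follow up timepoint as shown by Table 1 or 2 as applicable". Section 8.4 has sites review charts, identify eligible patients and then obtain consent. The post-operative period up to enrolment is therefore retrospective.

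**How events are counted.** Section 9 contains two rules.
- Conditions that exist when the subject is enrolled are pre-existing and are not recorded as adverse events unless they become more severe during the study.
- The closing sentence says that information on intra-operative and post-operative adverse events up to enrolment will be collected as well.

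Section 8.6 includes adverse events in the chart review. Section 10.5.1 sorts events into pretreatment, intraoperative and postoperative classes. Section 6.1 makes the rate of sight-threatening adverse events the primary safety endpoint, and Sections 10.2 and 10.5 analyse safety on enrolled, treated subjects.

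**Who is kept out.** The synopsis excludes ocular pathology which, in the investigator's judgment, "would either place the subject at increased risk of complications, contraindicate washout", or would "place the subject at risk of significant vision loss during the study period (e.g., wet age macular degeneration (AMD), corneal edema" (other examples follow). It does not distinguish pathology that preceded OMNI surgery from pathology that came after it.

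**The concern.** A pre-existing-condition rule normally stops a study from attributing to the treatment what the patient already had before it. It works when enrolment comes before treatment. Here the order is reversed, yet the rule is still tied to enrolment. A complication of the operation that lasts to the 24-month visit meets the wording of the rule and is removed.

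The events most exposed are those that last. A complication that resolved before enrolment does not exist at enrolment and is collected without difficulty. One that is permanent and stable is caught by the exclusionary sentence. For an endpoint concerned with threats to sight, leaving out the lasting events is the wrong way round.

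There is also a consistency problem. With up to 15 sites, one could follow the first rule and another the second, and the pooled rate would then depend partly on how each site read the text.

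**Working it through.** **1. The passages side by side.** Take an eye with a sight-threatening complication that begins after Day 0.

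| Status at enrolment | Pre-existing rule (Section 9) | Collection sentence (Section 9) | Result |
|---|---|---|---|
| Resolved | Does not apply | Collected | Counted |
| Present, later worsens | Recorded, because it worsened | Collected | Counted |
| Present and stable | Not recorded | Collected | Contradictory |

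Only the third row is in dispute. Section 10.5.1 offers a postoperative class, but a class is useful only once an event has been recorded. Tables 1 and 2 do not settle it either: their adverse event rows go from surgery straight to the 24-month visit, with no column for the interval between. Collection for that interval therefore rests on the Section 9 sentence and the chart review in Section 8.6.

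**2. The plan's own safety figure.** Section 10.1 says that with up to 130 subjects, events of about 3% frequency would be detected with 97.5% probability.
- P(at least one event) = 1 − (1 − 0.03)^130 = 98.1%.
- The rate giving exactly 97.5% is 1 − 0.025^(1/130) = 2.80%, which rounds to the stated 3%.

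The figure reproduces and is not disputed. It assumes that every event which occurs is recorded.

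**3. Effect of one eye.** 1/130 = 0.77 percentage points.

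**4. Effect of several eyes.** Assume, for illustration only, that 4 of 130 enrolled eyes had a sight-threatening post-operative event (4/130 = 3.1%, close to the 3% that Section 10.1 uses for adverse events in general). Exact (Clopper-Pearson) 95% intervals:

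| Of the 4, treated as pre-existing | Counted | Rate | Exact 95% CI |
|---|---|---|---|
| 0 | 4/130 | 3.1% | 0.8–7.7% |
| 1 | 3/130 | 2.3% | 0.5–6.6% |
| 2 | 2/130 | 1.5% | 0.2–5.4% |
| 3 | 1/130 | 0.8% | 0.02–4.2% |
| 4 | 0/130 | 0% | 0–2.8% |

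**5. Effect on the detection statement.** Let g be the assumed share of events left unrecorded as stable at enrolment. The recordable rate is 0.03(1 − g), and detection is 1 − [1 − 0.03(1 − g)]^130.
- g = 0.25: rate 2.25%, detection 94.8%.
- g = 0.50: rate 1.50%, detection 86.0%.
- g = 0.75: rate 0.75%, detection 62.4%.

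The documents give neither g nor a count of affected eyes, so steps 4 and 5 show sensitivity and are not estimates.

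**The case against.** The strongest defence is that Section 9 can be read consistently. The pre-existing rule follows a sentence about events during the trial, so it may be meant for the prospective phase only. The closing sentence then adds the retrospective events, Section 8.6 extracts them from charts, and Section 10.5.1 classifies them relative to treatment. On that reading a persisting post-operative event is collected once from the chart and is not entered again unless it worsens. This is plausible and may well be what was intended. But Section 9 does not state that precedence, and the literal wording of the pre-existing rule has no limit to prospective events. The objection limits the remedy to a clarification; it does not remove the need for one.

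It can also be said that the study is descriptive and that few eyes are likely to be affected. The first is correct. The second cannot be checked from the documents, and the primary endpoint is a rate in which single eyes matter.

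A reader might go further and infer that the synopsis exclusion has no reference date, or that it screens out eyes with surgical complications and so biases the safety rate downwards. The documents do not support either.
- **Timing.** The lead-in speaks of pathology being present, the risk is tied to the study period, and one element carries its own look-back, "active intraocular infection or inflammation within 30 days prior to Screening Visit". With Sections 8.3 and 8.4, this points to assessment at entry. Screening Visit is not a column in Table 1 or 2, but the table footnotes and Section 7.2 are not visible, so a definition may exist there.
- **Bias.** No screening counts are given, so size, direction and even the existence of a net bias are unknown. If event-free eyes were excluded more often than event eyes, the rate among enrolled eyes would be too high. Any study that consents patients about two years after surgery omits some of those treated, and the synopsis also requires that a subject "Is willing to return for required study follow-up visits".

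**Conclusion.** The counting rule in Section 9 is wrong as written for this design. It sets the pre-existing date at enrolment, 700 days or more after treatment, and conflicts with the sentence that collects post-operative events up to enrolment. Where the first rule is applied, the error runs in one direction: the primary safety rate is under-counted by 0.77 percentage points per affected eye at N = 130. How many eyes are affected is unknown and may be few or none. The conclusion rests only on visible text in Sections 2, 6.1, 8.3, 9 and 10.5.1; the illustrative event counts and shares are assumptions.

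The exclusion criterion is a separate and weaker matter. It does not distinguish onset before from onset after surgery, and the safety denominator contains enrolled subjects only. That limits what the rate describes, but it is not an error and no bias has been shown. Adding non-enrolled eyes back into the rate would not supply a bound: their charts may stop early, and the result would mix different lengths of follow-up.

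**What to change.** Amend Section 9 as follows.
1. For adverse event counting, define a pre-existing condition as one present before OMNI surgery (Day 0).
2. State that any condition with onset during or after surgery is recorded as an intraoperative or postoperative adverse event and counted in the safety rates, even if still present at enrolment.
3. State that such a condition is not entered a second time as a new prospective event unless it worsens.

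This matches the classes already in Section 10.5.1 and uses charts that Section 8.6 already has sites review. It adds no visits and changes neither eligibility nor the analysis population. The costs are a protocol text change with IRB review as needed, a short instruction to sites, and a check of any events already entered under the other reading. The safety rate may look slightly less favourable.

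Optional: each site could report an aggregate count of treated eyes that were not enrolled, by reason, noting for those excluded for ocular pathology whether it began before or after Day 0. The exclusion itself stays unchanged. A tally by reason is enough to show the extent of selection. A patient-level event log of non-enrolled eyes would need a waiver of authorization or de-identification, plus abstraction at up to 15 sites, which is out of proportion here. If Section 7.2 or the table footnotes already cover this, nothing more is needed.
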